3.2 Sample Size

The proposed study with 30 complete and evaluable subjects would have 80% power to detect a minimum effect size of 0.53. Based on literature reviews using 1.5% as the maximum standard deviation expected when measuring DHA levels in plasma, the study should be able to detect an absolute increase of at least 0.8% from the baseline DHA value after 90 days of RELiZORB use (i.e., a change from 3.0% at baseline to 3.8% after 90 administration days or a 27% relative increase). This sample size will be adequate to detect the desired 30% relative increase in DHA levels.

The primary efficacy endpoint for this study is the sum of DHA+EPA. The sample size was based on a literature review of DHA assuming an effect size of 0.53. Assuming the same effect size for measuring erythrocyte tissue composition of the total of DHA plus EPA is consistent with that of DHA, the current sample size will provide 80% power.

3.3 Subject Replacement

Approximately 30 to 40 subjects were to be enrolled in the study. Protocol compliant subjects from Protocol 0000497 were eligible for this study, unless clinical changes had occurred in which the patient no longer met the initial eligibility criteria.

Any subject who withdrew from the study before Study Visit 4 on Day 60 was to be replaced by an eligible subject unless enrollment was closed.

4. ANALYSIS AND REPORTING

4.1 Interim Analysis

No interim analysis is planned for this study.

4.2 Final Analysis

All final, planned analysis identified in the protocol and in this SAP will be performed after the last subject has completed the end of study visit (or early termination) and all relevant study data have been processed and integrated into the analysis data base (database lock). Any post-hoc, exploratory analysis completed to support planned study analysis, which were not identified in this SAP, will be documented and reported in appendices to the CSR. Any results from these unplanned analyses (post-hoc) will also be clearly identified as such.

5. ANALYSIS POPULATIONS

The following analysis populations are planned for this study

- Safety Population: The safety population includes all subjects who received at least one Relizorb exposure.
- Intent to Treat Population (ITT): The ITT population, includes all subjects who received at least one RELiZORB exposure. This population is the same as safety, and will be used for efficacy analyses.
- Per Protocol Population (PP): The per protocol population consists of all subjects who
 met the inclusion criteria, used RELiZORB as stated in the protocol and Instructions For
 Use (IFU) through at least Visit 3 (Day 30) and had not been the subject of any major
 protocol deviation(s).

Protocol: 0000498 Page 14 of 87

Final Version 3.0

6. GENERAL ISSUES FOR STATISTICAL ANALYSIS

6.1 General Statistical Methodology

The primary population for safety is the safety population. For the efficacy analysis, the primary endpoint will be conducted on both the per protocol (PP) and ITT populations. All secondary efficacy analyses will be conducted on the ITT population unless otherwise specified.

Continuous variables will be summarized using descriptive statistics, including number of nonmissing values, mean, standard deviation, median, minimum, and maximum. Qualitative variables will be summarized using the number and proportion of each possible value.

The minimum and maximum will be reported with the same degree of precision (i.e., the same number of decimal places with a maximum of 1 decimal place) as the raw data. Measures of location (mean and median) will be reported to 1 degree of precision (with a maximum of 2 decimal places) more than the raw data and the measure of spread (standard deviation) will be reported to 2 degrees of precision (with a maximum of 3 decimal places) more than the raw data. All efficacy endpoints in section 8.1 will use a maximum of two decimal places.

Categorical (qualitative) variable summaries will include the frequency and percentage of subjects who are in the particular category. The denominator for the percentage calculation will be based upon the total number of subjects in the relevant study population unless otherwise specified.

Assessments done on unscheduled visits will not be summarized but will be listed. If any assessments are repeated on the same day and/or time point, the last non-missing assessment will be summarized and/or analyzed.

Statistical tests will be conducted at the 0.05 significance level using 2-tailed tests, and nominal p-values will be reported. SAS software (SAS, Inc., Cary, NC) will be utilized for statistical analysis (version 9.3).

Subject level information presented in a listing will include subject identification number as well gender, age (examples: F/23, M/37). All listings will be sorted by subject identification numbers.

6.2 Handling of Missing Data

Available subject data will be used in the statistical analysis. For the MMRM analysis, subjects who lack all post-baseline measures, the baseline efficacy outcome will be imputed for all post-baseline responses (i.e., no change from baseline).

To handle missing or partial AE and medication dates, the following rules will be applied.

For partial start dates:

- 1. If the year is unknown, then do not impute the date but assign a missing value
- 2. If the month is unknown, then:
 - a. If the year matches the year of the first RELiZORB administration date, then impute the month and day of the first RELiZORB administration date.
 - b. Otherwise, assign "January."
- 3. If the day is unknown, then:

a. If the month and year match the month and year of the first RELiZORB administration date, then impute the day of the first RELiZORB administration date.

b. Otherwise, assign "01."

For partial end dates:

- 1. If the year is unknown, then do not impute the date but assign a missing value.
- 2. If the month is unknown, then assign "December."
- 3. If the day is unknown, then assign the last day of the month.

6.3 Derived Variables

The following derived variables have been initially identified as important for the analysis of the safety and efficacy endpoints. It is expected that additional variables will be required. The SAP will not be amended for additional variables that are not related to the primary target or key secondary target variables. Any additional derived or computed variables will be identified and documented in the SAS programs that create the analysis files. If the SAP is not amended, further derivations related to primary and secondary target variables will be described in the CSR.

- Baseline = the last non-missing measurement before the date of RELiZORB administration for safety assessments. For efficacy assessments, baseline will be the assessment collected at Visit 2 (Day 0). However, if the result from Visit 2 is missing and the result from Visit 1 is available, the result from Visit 1 will be used.
- Study Entry = Day -14, which occurs during Study Visit 1.
- Study day = Assessment Date Date of first RELiZORB administration (+ 1 if assessment date is on or after date of first RELiZORB administration).
- Change from Baseline = Value at Post Baseline Value at Baseline.
- % Change from Baseline = 100 * Change from Baseline / Value at Baseline.
- "End of Study" is the point at which the last contact with the subject during the protocolspecified schedule is made.
- "Screen Failure" is a subject who has not met eligibility criteria.

The years of enteral tube feeding will be calculated from the first date of gastrostomy tube placement in the medical history to the Visit 1 date. For partial dates, if the day is missing, the first will be used. If the month and day are missing, January 1 will be used. The years will be calculated as (Visit 1 date – date of gastrostomy tube placement)/365.25.

The following subgroups will be used for subgroup analyses of selected endpoints:

- Age Categories: <=12 years, 13-18 years, and >=19 years.
- CFRD Categories: CRFD and non-CFRD. CFRD will include all subjects who
 reported "cystic fibrosis related diabetes", "CFRD", "type 1 diabetes mellitus",
 "diabetes mellitus related to cystic fibrosis" in their medical history.

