# 4.9.9 Pregnancy Test

A serum  $\beta$ -hCG pregnancy test will be performed only for females of childbearing potential. Negative results must be available four days prior to the first Relizorb usage on Day 0. If a female subject becomes pregnant while participating in the study, the site is responsible for notifying the Alcresta Chief Medical Officer as soon as possible.

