# 4.9.10 Enteral Tube Feeding

During the treatment period (Days 0 to 90), subjects will receive enteral feedings using the same enteral formula, Impact Peptide 1.5. The volume of enteral tube feeding should be 500 to 1000 mL; subjects who routinely receive more or less volume may be enrolled only if approved by the Alcresta Chief Medical Officer. The enteral formula should be delivered using a compatible pump that has a no flow/low flow alarm at a flow rate set between 24 and 120 mL.

Title: Absorption and Safety with Sustained Use of Relizorb™ Evaluation (Assure) Study in Patients With Cystic Fibrosis Receiving Enteral Feeding

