3.1 Schedule of Events

Table 1: Schedule of Events

	Visit 1	Visit 2	Visit 3	Visit 4	Visit 5 *
Evaluation	Day -14	Day 0	Day 30	Day 60	Day 90
	Study Entry	Baseline	Treatment	Treatment	End of Study
Informed Consent	X				
Inclusion / Exclusion Criteria	X				
Demographics	X				
Medical History a	X				
Physical Examination	X				×
Height, Weight, Body Mass Index ^b	X	×	Х	X	×
Vital Signs c	X	×	×	X	×
Hematology d	×				×
Clinical Chemistry e	X				×
Urinalysis f	X				×
Blood Lipids 8	X	×	X	×	×
Serum Proteinsh	×	×	X	×	×
Serum Pregnancy Test (β-hCG)	X				
Urinary Leukotrienes	X	×	X	×	×
7-Day Gastrointestinal Symptom Diary	×	×	X	X	×
Plasma Fatty Acid Samples	×	×	X	X	×
Vitamins A, D, and E k	×	×	×	X	×
Peptamen 1.5 500 to 1000 mL ¹	X				
Impact Peptide 1.5 500 to 1000 mL		×	×	×	×
RELiZORB Administration			×		
RELiZORB Accountability Log			X		
Unanticipated Adverse Device Effects			X	, , , , , , , , , , , , , , , , , , ,	

Note: Tests and procedures should be performed according to the above schedule but changes in scheduled study visits (±4 days) are allowed with permission from the site for holidays, vacations, etc. The amount of blood taken from subjects will be limited to no more than 3 mL/kg in 24 hours and no more than 7 mL/kg over the course of the study.

CONFIDENTIAL

- If any Unanticipated Adverse Device Event (UADE) is reported on Day 90, then a safety follow-up telephone call will occur on Day 91, and the subject will be followed until either resolution of the event or for 30 days, whichever is shorter.
 - A complete medical history will be obtained.
 - Height and weight will be measured and recorded, and BMI will be calculated and recorded at each study visit. Four weight and BMI measurements recorded at 3 month intervals over the previous 12 months before Day -14 will be obtained from the medical record. b a
- Vital signs will include blood pressure, pulse rate, respiratory rate and oral/tympanic temperature and will be obtained on in-clinic days.
 - Hematology includes complete blood count and white blood cell differential. 5
- Clinical chemistry includes alkaline phosphatase, alanine aminotransferase (ALT), aspartate aminotransferase (AST), bicarbonate, blood urea nitrogen, calcium, chloride, cholesterol, creatinine phosphokinase, creatinine, glucose, lactate dehydrogenase, magnesium, phosphorus, potassium, sodium, total and direct bilirubin, and uric acid.

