9.7 Exposure to Treatment

The number of days of RELiZORB use for the overall treatment period, between Visits 2 and 3 (including Visit 2), between Visits 3 and 4 (including Visit 3), and between Visits 4 and 5 (including Visit 4 and 5) will be calculated. The average weekly number of days of RELiZORB use between these visits will be determined by first taking the number of days between Visits (date of last Visit – date of current visit +1) and dividing by 7. This will give us the number of weeks between Visits. Next, the number of days of RELiZORB use will be divided by the number of weeks between Visits to provide the average weekly RELiZORB use between Visits. Average weekly number of days of RELiZORB use for the overall treatment period will be calculated in the same manner.

Average volume of formula administered (mL/day) for the overall treatment period via RELiZORB is defined as the total volume of formula administered via RELiZORB across study / Number of days a RELiZORB administration occurred. Average volume between Visits 2 and 3 (including Visit 2), between Visits 3 and 4 (including Visit 3), and between Visits 4 and 5 (including Visit 4 and 5) will be calculated in the same manner as average volume for total study period except that the total volume of formula administered via RELiZORB / the number of days a RELiZORB administrations occurred between visits will be used.

Study treatment adherence will be calculated for each subject and summarized descriptively. Adherence will be defined as the number of days the RELiZORB is used divided by the number of days inclusive from Visit 2 through Visit 5, multiplied by 100. Adherence between visits will be summarized and defined as the number of days the RELiZORB is used between Visits (as defined in the first paragraph) divided by the number of days between Visits (Visits 2 and 3,

Visits 3 and 4, Visits 4 and 5), multiplied by 100.

The analysis will be completed using the safety population.

All RELiZORB usage information will be included in a subject listing.

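### The safety baseline rule in SAP 6.3, read literally, gives subjects who start RELiZORB on the Visit 2 date a Day -14 baseline and later starters a Day 0 baseline, so the descriptive lipid and vital-sign change columns mix the two

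*SAP*

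**What the plan says.** SAP 6.3 (Derived Variables) has two baseline rules. For safety it is "the last non-missing measurement before the date of RELiZORB administration for safety assessments". For efficacy it is different: "For efficacy assessments, baseline will be the assessment collected at Visit 2 (Day 0"), with Visit 1 used only if the Visit 2 result is missing.

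Several places put the planned start on the Visit 2 date:

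- Protocol 4.9.9 (Pregnancy Test) speaks of "first Relizorb usage on Day 0".
- Protocol 4.9.10 (Enteral Tube Feeding) states: "During the treatment period (Days 0 to 90), subjects will receive enteral feedings using the same enteral formula, Impact Peptide 1.5".
- SAP 9.7 (Exposure to Treatment) counts device use "between Visits 2 and 3 (including Visit 2"), so the Visit 2 day is an exposure day.
- The Peptamen 1.5 run-in ends on Day -1 in both schedules.

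The study-day formula in SAP 6.3 adds "1 if assessment date is on or after date of first RELiZORB administration". SAP 9.1 likewise assigns adverse events that begin on the first-administration date to RELiZORB.

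Both schedules of events label Visit 2 (Day 0) as Baseline and collect vital signs and blood lipids at all five visits. The SAP 3.1 footnote on vital signs reads: "Vital signs will include blood pressure, pulse rate, respiratory rate and oral/tympanic temperature and will be obtained on in-clinic days". Hematology, clinical chemistry and urinalysis are scheduled only at Day -14 and Day 90. SAP 9.3 and 9.4 call for actual values and changes from baseline, reported in Tables 14.3.4.4 (lipids) and 14.3.5.1 (vital signs).

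**The concern.** The safety rule works on dates and is strict. It does not include the date itself, and neither document has a time-of-day rule that would admit a clinic value taken before an evening feed. For a subject who follows the planned schedule, the Visit 2 value is excluded and the baseline drops back two weeks. For a subject whose first feed comes a day or more after the clinic visit, Visit 2 qualifies. The baseline visit then depends on when the first feed happened to take place.

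The two visits are not interchangeable. Day -14 is on the subject's usual formula. Day 0 follows a week on Peptamen 1.5, in which medium-chain triglycerides supply 10 g of the 14 g of fat per 250 mL (Protocol 11.1). A lipid change from Day -14 therefore includes any effect of moving to the run-in formula. The fatty acid results in the same report start from Day 0. In addition, the visit that the schedule calls Baseline would show its own change from baseline for Day 0 starters.

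**Working it through.** The plan states no figure for this point, so there is none to reproduce. The check applies the SAP 6.3 rules to the nominal visit days.

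**Inputs**

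- Lipid and vital-sign measurements: Days -14, 0, 30, 60 and 90 (schedule of events, both documents).
- Planned first use: Day 0 (Protocol 4.9.9 and 4.9.10; SAP 9.7).
- Safety rule: latest measurement with date < first-use date. SAP 6.3 omits the word first before administration; first use is the only workable reading.
- Study day = assessment date - first-use date, plus 1 if the assessment is on or after first use.

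**Results under the literal rule**

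| First use | Baseline visit | Study day of Visit 2 | Span to Day 30 | Span to Day 90 |
|---|---|---|---|---|
| Day 0 | Visit 1 (Day -14) | 0 - 0 + 1 = 1 | 30 - (-14) = 44 days | 90 - (-14) = 104 days |
| Day 1 | Visit 2 (Day 0) | 0 - 1 = -1 | 30 - 0 = 30 days | 90 - 0 = 90 days |
| Day 2 | Visit 2 (Day 0) | 0 - 2 = -2 | 30 days | 90 days |

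If Visit 2 values taken before the first feed count even on the same date, all three rows have a Day 0 baseline, with spans of 30 and 90 days.

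The 104 days equal the whole study in Protocol 4.2: 7 (observation) + 7 (run-in) + 90 (treatment) = 104. For a Day 0 starter the extra 14 days are the two pre-treatment weeks. They lengthen the span to Day 30 by 14/30 = 47% and the span to Day 90 by 14/90 = 16%. Visits may move by up to 4 days, so these spans are nominal.

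**Which outputs change**

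- Blood lipids and vital signs: measured at both Day -14 and Day 0, so the rule decides which is used.
- Chemistry, hematology and urinalysis: no Day 0 sample, so Day -14 under either wording.
- Fatty acids, vitamins, serum proteins and urinary leukotriene: governed by the efficacy rule, unaffected. Weight and BMI z-scores have their own Visit 2 baseline in SAP 6.3.1.2, with Visit 1 as fallback.

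**The case against.** The strongest reply is that little depends on this. SAP 9 makes safety descriptive, only two tables are affected, and no test uses their change columns. Actual values are reported beside the changes, so a reader who infers that the Day 0 measurement disappears from the report would be mistaken. All of that stands and limits the importance of the point.

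A second reply is that a usual-care reference is legitimate for safety. The protocol objectives compare tolerability with the observation week, and SAP 9.1 treats everything before first administration as standard of care. A uniform Day -14 baseline could be defended on that ground. The rule as written does not deliver one, because later starters get Day 0. SAP 10, which lists changes from the protocol's planned analysis, also names no deliberate change of safety baseline.

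A third reply is that few subjects may be affected. Feeds are usually nocturnal, and eligibility asks for only four to five feeding occasions a week, so first use may fall after the clinic date. It may; the documents do not say how often. A reader might infer that every subject is affected because Day 0 is the planned start, but a plan does not establish actual dates.

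Finally, a Day 0 baseline does not separate the device from everything else. At Day 0 subjects also change from Peptamen 1.5 to Impact Peptide 1.5 and stop PERT with feeds. This is correct: the gain from rewording is a uniform baseline and a 90-day span. Nor do the documents show that vital signs respond to a week on a different formula, so the formula argument applies to lipids.

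**Conclusion.** The point holds within a narrow scope. The literal SAP 6.3 rule yields a baseline that differs between subjects for blood lipids and vital signs: Day -14 (104 days to Day 90) for Day 0 starters, and Day 0 (90 days) for later starters. It also conflicts with the schedule's own Baseline label for Visit 2. The mixture appears in the change-from-baseline columns of Tables 14.3.4.4 and 14.3.5.1.

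The share of subjects affected lies anywhere from 0 to 100%, with Day 0 the planned start. At 0% every subject with a Visit 2 value has a Day 0 baseline; at 100% all have Day -14. The columns are mixed only in between. The size of any shift in the means cannot be derived from the documents.

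A reader might go further and infer that the primary result or the safety laboratory tables in general are compromised. The documents do not support that. The efficacy baseline is defined separately as Visit 2, and chemistry, hematology and urinalysis have a single pre-treatment sample. The conclusion assumes that administration in SAP 6.3 means first administration and that the rule would be programmed as worded.

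**What to change.** Reword the safety baseline in SAP 6.3 as: the last non-missing measurement taken before the first RELiZORB administration, counting Visit 2 (Day 0) values obtained before the first RELiZORB feed even if they fall on the same date, with Visit 1 as fallback, as for efficacy.

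Simply extending the rule to include the date of first use would be weaker, because it could admit a value taken after a feed on that date. Device training at Visit 2 makes it likely that assessments come first. However, Protocol 4.3 allows supplies to arrive before Day 0, and no section requires assessment before the first feed. The SAP should therefore say how the order is established if times are not recorded.

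The cost is one sentence and no new data. There is a small downside: cholesterol in the chemistry panel keeps a Day -14 baseline while total cholesterol in the lipid panel uses Day 0, so the two tables need a footnote. A further note should say that changes from Day 0 also reflect the formula switch and the end of PERT with feeds.

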6.3.1 Weight and BMI Derived Variables

Up to 4 weight, height, and body mass index (BMI), (and BMI percentile for subjects of age ≤18 years) recordings will be obtained from the medical record at approximately 3 month intervals over the previous 12 months prior to Visit 1 on Day -14. Weight and BMI will be collected at Visit 1 (study entry; Day -14) and at study visits on Day 0 (Visit 2), Day 30 (Visit 3), Day 60 (Visit 4), and Day 90 (Visit 5).

6.3.1.1 Weight Gain Velocity

Weight gain velocity (WGV) is defined as the rate of change in body weight per initial body weight per time period. The quantity will be expressed in units of g/kg/90 days.

The formula to calculate WGV between two dates Date1 and Date2 is:

90 x [weight (g) at Date2 – weight (g) at Date1] / [weight (kg) at Date1] / (Date2 – Date1 + 1)

The factor of 90 converts the rate from per day to per 90 days.

The WGV can be considered the slope as the change in weight (Δ w) divided by the change in days plus 1 (Δ t). This quantity is multiplied by 90 and then divided by the subject weight at interval start (kg) to express the results as 90-day changes for each kilogram of weight. For example, if a patient is 62.0 kg on January 1, 2016 and 63.5 kg on April 1, 2016, the slope is 1.5 kg/92 days = 1.5 kg/92 days = 1500 g/92 days = 16.3 grams per day. Equivalently, 90 days x 16.3 g/day equals 1467.4 g / 90 days. Expressed per kg body weight, the WGV equals 23.7 g/kg/90 days. Equivalently, as above, 90*(63500-62000)/62.0/92 = 23.7

WGV will be calculated from the date of Visit 2 to the date of Visit 5, or the last visit at which a weight is available.

The historical weight recordings will be used to calculate historical WGV. Any weights recorded more than 12 months before Study Entry and weights recorded before the date of tube placement indicated in medical history will be excluded. The selection of the appropriate medical indications and date imputations for this are described in Section 6.3 for the calculation of duration of enteral feeding. The historical WGV will be determined by first calculating the change in weight between each consecutive historical weight recorded before Study Entry and thus providing up to 3 values for change in weight. WGV will then be calculated from these weight changes as described above. The average of these values will be determined and identified as the average historical WGV.

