## 7.5 Procedures for Handling Missing, Unused and Spurious Data

All available safety and tolerability data will be presented in data listings and tabulations. No data imputation will be applied for missing values. The relevance of missing sample data will be assessed. Data that are potentially spurious or erroneous will be examined according to standard data management operating procedures.

In the case of subject withdrawal from the study, data collected at the Day 30 and Day 60 time point will be employed in the analysis of that time point but those values will not be carried forward.

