## 7.8 Efficacy Analysis

The measurement of the absorption of fats is an important efficacy endpoint, using absorption of fatty acids as surrogate biomarkers for fat absorption. LCPUFA plasma concentrations such as DHA and EPA will be an outcome variable, along with tissue accretion of LCPUFAs, measured as relative levels in erythrocyte membrane, and the profile of fatty acids in plasma. The fatty acid profile will also be used to calculate the ratio of omega-6 to omega-3 fatty acids, another outcome variable. Fat-soluble vitamin (A, D, and E) concentration is an additional efficacy endpoint and will be used as a laboratory outcome variable. Serum protein (total protein, prealbumin, albumin, and transferrin) concentrations and urinary leukotriene concentrations are additional endpoints and also represent laboratory outcome variables.

For all laboratory outcome variables, mean values from samples obtained on Day -14 and Day 0 will be compared using a two-sided test for comparison. The mean value from samples obtained on Day 0 will be used as the baseline for comparison with mean values from samples obtained on Days 30, 60, and 90 using ANOVA.

Body weight, height, and BMI are endpoints and clinical outcome variables. Absolute change in body weight from Day 0 through Days 30, 60, and 90 will be analyzed using ANOVA. To evaluate the effect of Relizorb use on weight and BMI, up to 4 weight and BMI recordings obtained from the medical record at 3 month intervals over the previous 12 months. The historical weight recordings will be used to calculate historical weight gain velocity, expressed as grams of body weight per kilogram of body weight per day. The study weight gain velocity will be similarly calculated by using the body weight values obtained on Days 0, 30, 60, and 90. The historical weight gain velocity will be compared to the study weight gain velocity using a two-sided test for comparison. In addition, the historical weight and BMI recordings, along with the weight and BMI values recorded on Day 0, will be used to calculate a standard score for weight and BMI values recorded on Days 30, 60, and 90.

Title: Absorption and Safety with Sustained Use of Relizorb™ Evaluation (Assure) Study in Patients With Cystic Fibrosis Receiving Enteral Feeding

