12.3 Planned Figure Descriptions

The following are planned summary figures for protocol 0000498:

Figure Number	Population	Title	Reference Table
14.2.1.1	Per Protocol	Boxplot of Erythrocyte Membrane Fatty Acid Composition (%) for EPA, DHA and DHA plus EPA (%)	14.2.1.1a
14.2.1.2	Per Protocol	Boxplot of Plasma Fatty Acid Concentration (μg/mL) for Total EPA, Total DHA, and Total EPA+DHA (μg/mL)	14.2.2.1b
14.2.1.12	Per-Protocol	Boxplot of Weight and Body Mass Index (BMI) Z-scores	14.2.1.10
14.2.1.13	Per-Protocol	Boxplot of Weight Gain Velocity (g/kg/30 days)	14.2.1.11

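### Weight gain velocity divides by one day more than the elapsed time, and an early withdrawer's short-interval rate counts equally in the 0-90 day comparison (minor, exploratory endpoint)

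*SAP*

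**What the plan says.** SAP 6.3.1.1 defines weight gain velocity (WGV) as 90 × (weight change in g) / (starting weight in kg) / (Date2 − Date1 + 1). It describes the result as a slope, "divided by the change in days plus 1", and adds: "The factor of 90 converts the rate from per day to per 90 days". The worked example reads "if a patient is 62.0 kg on January 1, 2016 and 63.5 kg on April 1, 2016, the slope is 1.5 kg/92 days" and ends at 23.7 g/kg/90 days.

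On-study WGV uses two weights, "from the date of Visit 2 to the date of Visit 5, or the last visit at which a weight is available". Historical WGV is the mean of up to three consecutive-interval values from the same formula, at intervals of about 3 months. SAP 8.3.1 tests the change from the historical average to 0-90 days within age subgroups, by one-sample t-test or Wilcoxon signed rank test, without weighting for interval length. SAP 2.2.2 lists the endpoint as exploratory.

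Protocol 7.8 expresses velocity per day and says: "The study weight gain velocity will be similarly calculated by using the body weight values obtained on Days 0, 30, 60, and 90". For withdrawers, protocol 7.5 says Day 30 and Day 60 data "will be employed in the analysis of that time point but those values will not be carried forward".

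SAP Section 10, which lists changes from the protocol, does not mention velocity. The planned boxplot of WGV (Figure 14.2.1.13, SAP 12.3) is on a 30-day scale, while the table it refers to (14.2.1.11) is on a 90-day scale.

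**The concern.** A rate of change should be divided by the time over which the change took place. Adding a day understates the rate, and more so over a short interval than a long one, so subjects with different follow-up are not treated alike. At the extreme, a subject with no weight after Visit 2 could be given a velocity of zero, which looks like an observation but contains no information.

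The last-available-weight rule raises a second question. A 30-day change is multiplied by nearly three to reach the 90-day scale, and its weighing error is multiplied with it. That subject then counts the same as a completer in a test run within small age groups. At stake is how the velocity result can be read: whether a subgroup mean labelled 0-90 days reflects 90 days of follow-up or partly extrapolated shorter intervals.

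**Working it through.** **Inputs.** The formula, the example and the two-weight rule are from SAP 6.3.1.1; the test is from SAP 8.3.1; the visit days are from the schedule of events. Not in the documents and therefore assumed: historical intervals of 91 days (SAP: about 3 months), independent weighing error with the same SD at each visit, and the values stated in steps 4 and 5.

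**1. Reproduce the example.** With divisor 92: 90 × 1500 / 62.0 / 92 = 23.67, the stated 23.7. From 1 January to 1 April 2016 (a leap year) is 91 elapsed days. With divisor 91: 90 × 1500 / 62.0 / 91 = 23.93. Ratio 91/92, or −1.1%.

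**2. Size of the extra day.** The formula returns L/(L+1) of the true rate over L days. Relative to a historical interval of 91 days, which carries 91/92, the net factor is [L/(L+1)] / (91/92).

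| L (days) | Understatement | Net of historical |
|---|---|---|
| 30 | −3.2% | −2.2% |
| 60 | −1.6% | −0.6% |
| 90 | −1.1% | −0.01% |

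For completers both velocities shrink by practically the same factor, so the difference and its SD shrink together and the t-test is unaffected. For a Day 30 withdrawer with an unchanged true rate of 24 (illustrative), the on-study value is 24 × 30/31 = 23.23 and the historical value 24 × 91/92 = 23.74, a spurious difference of −0.51 g/kg/90 days.

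**3. No weight after Visit 2.** If the last available weight is taken to be Visit 2 itself, Date2 = Date1 and the formula gives 90 × 0 / weight / 1 = 0. With elapsed days it is 0/0, which is properly missing. The SAP does not say whether such a subject is included.

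**4. Scaling of short follow-up.** The observed change is multiplied by 90/31 = 2.90 at Day 30, 90/61 = 1.48 at Day 60 and 90/91 = 0.99 at Day 90. Weighing-error variance relative to a completer is (91/31)² = 8.6 at Day 30 and (91/61)² = 2.2 at Day 60. Extrapolation also assumes a constant rate: an assumed 30 kg subject who gains 0.6 kg by Day 30 and then stays level has WGV 90 × 600/30/31 = 58.1 if withdrawn at Day 30, but 90 × 600/30/91 = 19.8 if followed to Day 90.

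**5. Effect on precision.** Assume a weighing SD of 0.5 kg and a group of 11 with one Day 30 withdrawer. Error SD = 90 × 500 × √2 / weight / (L+1). At 30 kg this is 23.3 (Day 90) and 68.4 (Day 30); at 62 kg, the weight in the SAP's example, it is 11.3 and 33.1. With between-subject SD b,

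- SE including the withdrawer = √[10 × (SD90² + b²) + (SD30² + b²)] / 11
- SE omitting the withdrawer = √[(SD90² + b²)/10]

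| Weight | b | SE including | SE omitting | Change |
|---|---|---|---|---|
| 30 kg | 0 | 9.14 | 7.37 | +24% |
| 30 kg | 20 | 10.95 | 9.71 | +13% |
| 30 kg | 40 | 15.13 | 14.64 | +3% |
| 62 kg | 20 | 7.48 | 7.26 | +3% |
| 62 kg | 40 | 12.85 | 13.14 | −2% |

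These SEs cover the on-study part of the difference only.

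**6. Two weights or four, for completers.** In units of weighing SD and on elapsed days, the two-point change has SD √2 = 1.41. A least-squares slope through Days 0, 30, 60 and 90 has 90/√(45² + 15² + 15² + 45²) = 90/√4500 = 1.34. The two middle weights are worth about 5% in SD.

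**The case against.** **The extra day is a declared convention.** It is given in the formula, in words and in the example, and it matches the inclusive counting used for study day (SAP 6.3) and exposure (SAP 9.7). This stands as an explanation, and the net effect is indeed small. But inclusive counting suits a count of days on treatment. A slope needs elapsed time, and two weights exactly 90 days apart should return the observed change per kg, not 90/91 of it.

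**A zero for a subject without later weights could be deliberate**, in line with the no-change imputation in SAP 6.2. That rule is stated only for the repeated-measures model, so it does not settle the matter for velocity.

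**A reader might infer that the last-available-weight rule breaches the protocol's ban on carrying values forward.** The documents do not support that. No Day 30 weight is placed at Day 90, the actual dates are used, protocol 7.8 defines velocity as a per-day rate and gives no rule for withdrawers, and SAP 6.2 says available data will be used. What remains is that a shorter-interval rate sits under a 0-90 day label.

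**A reader might also infer that one withdrawer always costs precision.** The 24% figure needs no true variation in growth between subjects, which is implausible from age 4 with no upper limit. The sign changes within the range above, and the signed rank option in SAP 8.3.1 limits the influence of one extreme value.

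**Using two weights loses little.** The protocol only says that study velocity is calculated similarly to the historical one. A mean of consecutive intervals nearly reduces to the first and last weights, and regression gains about 5%. The undeclared difference in wording stands; a material loss of information does not.

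**Conclusion.** The concern holds as a minor point. The divisor is one day too long, and the example should read 23.9 instead of 23.7 g/kg/90 days. The bias is 1.1% at 90 days and 3.2% at 30 days. Assuming historical intervals of about 91 days, it cancels for completers and leaves about −2% for a Day 30 withdrawer. The possible exact zero for a subject with no later weight is a gap that the SAP should close.

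Equal weighting of extrapolated rates is real: with equal, independent weighing errors, error variance is about 8.6 times a completer's at Day 30 and 2.2 times at Day 60. Its effect on the SE runs from +24% to −2% over the assumed body weights and between-subject SDs, so no firm loss can be claimed. The documents do not give the number of early withdrawers or the age-group sizes. Nor do they show that a random-slope model is needed; in small age groups it may be hard to fit, and on log weight it would change the quantity being estimated.

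WGV is exploratory with nominal p-values, so no primary or secondary result is affected.

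**What to change.** 1. In SAP 6.3.1.1, divide by Date2 − Date1. Correct the example throughout: 1500/91 = 16.5 g per day, 90 × 1500/91 = 1483.5 g per 90 days, and 1483.5/62.0 = 23.9 g/kg/90 days. Apply the same formula to historical intervals.
2. State that on-study WGV requires at least one weight after Visit 2 and is otherwise missing.
3. Keep the available-data analysis in the ITT population. Add a sensitivity analysis limited to subjects with a Visit 5 weight, and show withdrawers' velocities separately with their interval lengths. Because the sensitivity analysis conditions on completion, it should accompany the ITT analysis and not replace it.
4. In SAP Section 10, list the two-weight calculation and the last-available-weight rule as changes from protocol 7.8.
5. Put Figure 14.2.1.13 on g/kg/90 days, to match Table 14.2.1.11.

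The cost is SAP wording, one line of code and one extra table. No new data are needed.
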